8.1 Lenalidomide Dose Modifications

Lenalidomide (Cycle 1: Day 1-14 Cycle 2-6: Day 1-21)	
Starting dose	25mg
-1	10 mg
-2	Discontinue

→ → Use the NCI Common Terminology Criteria for Adverse Events (CTCAE) version 5.0*
unless otherwise specified ← ←

CTCAE System/Organ/Class (SOC)	ADVERSE EVENT	AGENT	ACTION**
Investigations	Platelet count decreased Grade 4	Lenalidomide	
*Omit dose until AE has resolved to Grade 1 or better
 
 • Follow CBC weekly • If thrombocytopenia $<30,000/\text{mm}^3$ recurs, reduce dose by one dose level (by 5 mg) and continue therapy when platelet count $\geq 30,000/\text{mm}^3$ 
If, after lenalidomide has been omitted, and the AE does not return to \leqGrade 1 within 4 weeks, then the patient may continue on remaining agent(s) till the completion of maintenance and then proceed to off study

	Neutrophil count decreased Grade 4		
*Omit dose until AE has resolved to Grade 2 or better
 
 • Follow CBC weekly * If neutropenia has resolved to \leqGrade 2, resume dose at one level lower *If, after lenalidomide has been omitted, and the AE does not return to \leqGrade 2 within 4 weeks, then the patient may continue on remaining agent(s) till the completion of maintenance and then proceed to off study
Blood and lymphatic system disorders	Anemia Grade 4		
*Omit dose until AE has resolved to Grade 2 or better
 
 • Follow CBC weekly * If anemia has resolved to \leqGrade 2, resume dose at one level lower *If, after lenalidomide has been omitted, and the AE does not return to \leqGrade 1 within 4 weeks, then the patient may continue on remaining agent(s) till the completion of maintenance and then proceed to off study
	Febrile neutropenia \geq Grade 3		
 • Omit dose and follow CBC weekly • If neutropenia has resolved to \leqGrade 2, resume dose at same level with GCSF support (See Section 9.2)

CTCAE System/Organ/Class (SOC)	ADVERSE EVENT	AGENT	ACTION**
Cardiac disorders	Sinus bradycardia/ other cardiac arrhythmia Grade 2	Lenalidomide	Omit dose and follow at least weekly until resolution 
 • If AE resolves to \leqGrade 1, reduce dose by one dose level and continue therapy
	\geq Grade 3		
 • Discontinue study treatment and go off study

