2. Hematologic toxicity (neutropenia and thrombocytopenia)
3. Deep Venous Thrombosis and Pulmonary Embolism

Common known potential toxicities, > 10%:

Cardiovascular: Peripheral edema
Central nervous system: Fatigue, pyrexia, dizziness, headache
Dermatologic: Pruritus, rash, dry skin
Endocrine & metabolic: Hyperglycemia, hypokalemia
Gastrointestinal: Diarrhea, constipation, nausea, weight loss, dyspepsia, anorexia, taste perversion, abdominal pain
Genitourinary: Urinary tract infection
Hematologic: Thrombocytopenia, neutropenia, anemia, myelosuppression is dose-dependent and reversible with treatment interruption and/or dose reduction
Infection, especially when white blood cell count is low
Neuromuscular & skeletal: Muscle cramp, arthralgia, back pain, tremor, weakness, paresthesia, limb pain, muscle spasms
Ocular: Blurred vision
Respiratory: Nasopharyngitis, cough, dyspnea, pharyngitis, epistaxis, upper respiratory infection, pneumonia, shortness of breath

Less common known potential toxicities, 1% - 10%:

Cardiovascular: Edema, deep vein thrombosis, hypertension, chest pain, palpitation, atrial fibrillation, syncope
Central nervous system: Insomnia, hypoesthesia, pain, depression
Dermatologic: Bruising, cellulitis, erythema
Endocrine & metabolic: Hypothyroidism, hypomagnesemia, hypocalcemia
Gastrointestinal: Vomiting, xerostomia, loose stools
Genitourinary: Dysuria
Hematologic: Leukopenia, febrile neutropenia, Lymphopenia
Hepatic: ALT increased, abnormal hepatic function tests
Neuromuscular & skeletal: Myalgia, rigors, neuropathy
Respiratory: Sinusitis, rhinitis, bronchitis, pulmonary embolism
Miscellaneous: Night sweats, diaphoresis, fever

Rare known potential toxicities, <1% (Limited to important or life-threatening):

Angioedema, Stevens-Johnson Syndrome and Toxic Epidermal Necrolysis, Tumor Lysis Syndrome, Graft vs. Host Disease, rhabdomyolysis, Kidney damage which may require dialysis

15.18 **Drug procurement:** Commercial supplies. Pharmacies or clinics shall obtain supplies from normal commercial supply chain or wholesaler.

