16.2 Statistical Design

Due to the lack of data to identify relevant biomarkers, the estimation of RR would be of interest. In each group, the response rates will be examined to see if there's any preliminary evidence to suggest further studies. This study will not utilize a formal statistical design.

For each biomarker category, the RR will be estimated by the number of patients who achieve a PR or better divided by the total number of evaluable patients in each cohort. Exact binomial 95% confidence intervals for these rates will be calculated.

16.22 Sample Size: A maximum of 30 evaluable patients will be accrued in cohort A and B and 60 patients in cohort C and D respectively. We anticipate accruing an additional 2 in cohort A and B and 3 in cohort C and D to account for ineligibility, cancellation, major treatment violation, or other reasons. Therefore, the maximum projected accrual is 190 patients (A: 32, B: 32, C: 63 and D: 63).

16.23 Accrual Rate and Study Duration: The anticipated accrual rate is 6 evaluable patients per month. Therefore, the accrual period for this pilot study is expected to be approximately 32 months. The final analysis can begin approximately 35 months after the trial begins, i.e. as soon as the last patient has been observed for 1 months and allowing 2 months for data entry.

16.24 Other considerations: Adverse events, quality/duration of response, and patterns of treatment failure observed in this study, as well as scientific discoveries or changes in standard care will be taken into account in any decision to terminate the study

16.3 Analysis Plan.

The analysis for this study is planned to start after data maturity has occurred. It is anticipated that the earliest date in which the result will be available via manuscript, abstract or presentation after the last registered patient has been followed for at least 1 month.

16.31 Primary Outcome Analyses:

Each cohort (A-D) will be evaluated separately and independently.

16.311 Definition:

The primary endpoint of this study is RR after 1 cycle of treatment. RR is defined as a binary variable. A success will be defined as patient who achieve a response of a PR or better using the IMWG criteria (Section 11.0) after one cycle of treatment. All patients meeting eligibility criteria who have signed a consent form, who complete at least one cycle of treatment and have successfully submitted biospecimens (pre and post treatment) will be evaluable for the endpoint.

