16.32 Secondary Outcome Analyses

16.321 Biomarkers and RR will be analyzed using logistic regressions to identify predictive biomarkers.

16.322 RR among African American (AA) patients and white MM patients will be evaluated after one cycle of treatment. Chi-Square (or Fischer Exact) test and 95% confidence intervals will be estimated to compared AA and white patients descriptively.

16.323 Correlation between the depth of hematological responses and biomarkers will be estimated. Logistic regressions and chi square (or Fischer exact) testing will be utilized.

16.33 Data & Safety Monitoring:

The principal investigator(s) and the study statistician will review the study at least twice a year to identify accrual, adverse event, and any endpoint problems that might be developing. The Mayo Clinic Cancer Center (MCCC) Data Safety Monitoring Board (DSMB) is responsible for reviewing accrual and safety data for this trial at least twice a year, based on reports provided by the MCCC Statistical Office.

Adverse Event Stopping Rules: (Each cohort will be analyzed separately) The stopping rules specified below are based on the knowledge available at study development. We note that the Adverse Event Stopping Rule may be adjusted in the event of either (1) the study re-opening to accrual or (2) at any time during the conduct of the trial and in consideration of newly acquired information regarding the adverse event profile of the treatment(s) under investigation. The study team may choose to suspend accrual because of unexpected adverse event profiles that have not crossed the specified rule below.

Accrual will be temporarily suspended to this study if at any time we observe events considered at least possibly related to study treatment (i.e. an adverse

event with attribute specified as “possible”, “probable”, or “definite”) that satisfy either of the following:

- If 3 or more out of the first 10 treated patients experience grade 4+ non-hematological toxicities
- If after the first 10 patients have been treated, 30% of patients experience grade 4+ non-hematologic toxicities

We note that we will review grade 5 adverse events deemed “unrelated” or “unlikely to be related”, to verify their attribution and to monitor the emergence of a previously unrecognized treatment-related adverse event.

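### Section 16.33's mandatory accrual pause has no separate trigger for treatment-related deaths and does not count a fatal event classed as hematologic

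*Combined protocol and SAP*

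**What the plan says.** The Adverse Event Stopping Rules in section 16.33 open with "Accrual will be temporarily suspended to this study if at any time we observe events considered at least possibly related to study treatment" and then give two limbs. The early limb is worded "If 3 or more out of the first 10 treated patients experience grade 4+ non-hematological toxicities", and the limb that governs the rest of accrual is worded "If after the first 10 patients have been treated, 30% of patients experience grade 4+ non-hematologic toxicities".

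They are headed by the note "Each cohort will be analyzed separately". Counting is therefore by cohort, while the pause, read literally, applies to the whole study.

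The section's one sentence on deaths, which contains "we will review grade 5 adverse events deemed", concerns only deaths attributed as unrelated or unlikely. It sets no threshold and no action.

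The plan does not define non-hematologic. Section 8.1 lists febrile neutropenia under "Blood and lymphatic system disorders", and section 15.17 also lists it among hematologic toxicities. Section 15.17 carries a boxed warning for "Hematologic toxicity (neutropenia and thrombocytopenia)".

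Section 10.32 exempts anemia and four blood-count decreases from expedited reporting, but only up to grade 4 and only where the event does not lead to hospitalization.

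**The concern.** The rule is the only place in the plan where an observed toxicity count obliges anyone to stop enrolling. It has two gaps at the most severe end.

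First, a death judged related carries the same weight as a reversible grade 4 event and is measured against the same 30% bar. That bar is identical for untreated smoldering patients (cohort A), who are defined by the absence of listed myeloma abnormalities, and for relapsed patients.

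Second, the restriction to non-hematologic events has no upper grade limit. A fatal event classed as hematologic therefore falls outside the count, although this is a toxicity for which lenalidomide carries a boxed warning.

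A team following section 16.33 to the letter could keep enrolling after several related deaths without being required to pause.

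**Working it through.** **Inputs.** The two limbs, the attribution requirement and the per-cohort counting come from section 16.33. Section 16.22 gives the cohort sizes: "the maximum projected accrual is 190 patients (A: 32, B: 32, C: 63 and D: 63". Section 10.623 equates grade 5 with death. The plan states no operating characteristics for the rule and no tolerated toxicity rate, so the event rates below are assumptions.

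**Step 1: the plan's own figures.** 3/10 = 30%, so the two limbs agree at the tenth patient. 32 + 32 + 63 + 63 = 190. Both reproduce.

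**Step 2: the boundary.** With n patients treated in a cohort, the rule is crossed when the number with a counted event reaches b(n) = 3 for n ≤ 10, and b(n) = 0.30 × n rounded up for n > 10.

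| n treated | b(n) | Largest count that does not cross |
|---|---|---|
| 10 | 3 | 2 (20.0%) |
| 30 | 9 | 8 (26.7%) |
| 31 | 10 | 9 (29.0%) |
| 32 | 10 | 9 (28.1%) |
| 63 | 19 | 18 (28.6%) |

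Because the rule is checked at any time, the count must stay below the boundary throughout. Stepping through n = 1 to 32 shows that 9 is reachable: at most 2 by n = 10, at most 8 by n = 30, and the ninth at n = 31. If only 30 are treated the maximum is 8. For 63 treated it is 18. All of these patients could have died of related non-hematologic events, provided that nobody else has a counted event.

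**Step 3: chance of crossing.** Let p be the true rate of related fatal non-hematologic events, with no other counted events and patients independent. For the first ten alone, P(3 or more) = 1 − Σ C(10,k) p^k (1−p)^(10−k), summed over k = 0 to 2. For the whole rule, let f(n,x) be the probability of x events after n patients without having crossed. Then f(n,x) = (1−p) f(n−1,x) + p f(n−1,x−1) for x < b(n), and the crossing probability is 1 minus the sum of f(N,x) over x.

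| p | First 10 | By n = 32 | By n = 63 | P(at least 2 deaths in 32) |
|---|---|---|---|---|
| 5% | 1.15% | 1.22% | 1.22% | 48% |
| 10% | 7.0% | 8.0% | 8.0% | 84% |
| 15% | 18.0% | 22.0% | 22.3% | 96% |

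**Step 4: any of the four cohorts.** A crossing in one cohort suspends the study. With the same p in all four at full accrual, P(at least one crosses) = 1 − (1 − P32)² (1 − P63)²:

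- p = 5%: 1 − 0.9878⁴ = 5%
- p = 10%: 1 − 0.9198² × 0.9197² = 28%
- p = 15%: 1 − 0.7798² × 0.7774² = 63%

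**Step 5: fatal hematologic events.** No calculation is needed. An event classed as hematologic adds nothing to either limb at any grade. Set beside this, section 10.32 treats a hematologic event as routine only at grade 4 or below and without hospitalization. Section 16.33 has no such ceiling.

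**The case against.** Several counter-arguments have force.

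- **Deaths are in the rule.** A reader might infer that related deaths have no trigger at all. The text does not support that: grade 4+ includes grade 5, and the figure of 9 depends on it. What is missing is a separate trigger.
- **Nine is not a cap on related deaths.** It covers non-hematologic deaths only and rests on the conditions in Step 2. The extra 2 patients in cohorts A and B allow partly for cancellations, and under section 13.6 a cancelled patient receives no treatment, so 8 may be the relevant figure.
- **Not all marrow-related deaths are excluded.** A reader might infer that fatal marrow toxicity is never counted. The plan does not establish this. Non-hematologic is undefined; section 8.1 files neutrophil and platelet decreases under Investigations, so organ class alone cannot be the dividing line; and section 15.17 lists infection with a low white count apart from the hematologic terms. Febrile neutropenia coded as such is the clear case.
- **Other safeguards exist.** Section 16.33 allows discretionary suspension and adjustment of the rule at any time, and requires review by the investigators and statistician and by the DSMB at least twice a year. Sections 10.41 and 10.52 call for 24-hour reporting of deaths, section 13.3 allows discontinuation for safety at any time, and section 16.24 brings adverse events into any decision to terminate.
- **The assumed rates are illustrative.** Nothing in the plan predicts 5% to 15% related mortality with no related grade 4 events.

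These points limit the wording and soften the consequence. They do not close the gap: none of the safeguards obliges a pause after a related death, and none brings a fatal hematologic event into the count. At the planned 6 evaluable patients per month, the minimum six-month review interval spans about 6 × 6 = 36 evaluable patients across the trial.

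**Conclusion.** The point holds in limited form. Section 16.33 gives related deaths no trigger of their own and leaves out a fatal event classed as hematologic, whereas section 10.32 draws its line at grade 4.

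For non-hematologic deaths the boundary permits 9 among 31 or 32 treated in cohort A or B, 8 among 30, and 18 among 63 in C or D. These figures assume no other counted event and an order of occurrence that stays under the boundary. They describe what the rule allows and are not a forecast. At assumed related-death rates of 5%, 10% and 15%, a single 32-patient cohort crosses with probability 1%, 8% and 22%. The chance that at least one cohort crosses and so suspends the study is 5%, 28% and 63%, if all four share the rate and fill.

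This is a weakness in the protection the rule offers, and it is cheap to repair. It does not show that the trial lacks safety oversight.

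**What to change.** In section 16.33:

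1. Define the counted event as *grade 4+ non-hematologic, or grade 5 of any organ class, at least possibly related to study treatment*.
2. Add a third condition: any grade 5 event at least possibly related to study treatment triggers prompt review by the study team and the DSMB, and accrual to at least the affected cohort is paused until that review is complete.
3. Keep the 3-of-10 and 30% limbs otherwise unchanged. A death reviewed under item 2 still counts toward them once accrual resumes.

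The change is to protocol wording. Section 10.41 already requires initial notice of grade 4 and 5 serious events within 24 hours, so no new data flow is needed.

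The cost is short accrual pauses, which may not be rare in the relapsed cohorts. The probability of at least one pause in N patients is 1 − (1 − q)^N, where q is the related-death rate. For N = 63 it is 1 − 0.99^63 = 47% at an assumed q of 1%, and 1 − 0.98^63 = 72% at 2%. For N = 32 the figures are 1 − 0.99^32 = 28% and 1 − 0.98^32 = 48%. The sponsor should accept this knowingly and arrange for the review to be quick.

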16.4 Inclusion of Women and Minorities

16.41 This study will be available to all eligible patients, regardless of race, gender, or ethnic origin.

16.42 There is no information currently available regarding differential effects of this regimen in subsets defined by race, gender, or ethnicity, and there is no reason to expect such differences to exist. Therefore, although the planned analysis will, as always, look for differences in treatment effect based on racial and gender groupings, the sample size is not increased in order to provide additional power for subset analyses.

16.43 Based on prior studies involving similar disease sites, we expect about 3-5% of patients will be classified as minorities by race. However, we are aiming to increase these percentages and accrue 15% of African American patients to meet our secondary endpoints. If efforts to accrue in this racial category are not fruitful, the study will continue to accrue patients in the other racial categories. . Expected sizes of racial by gender subsets are shown in the following table:

Accrual Estimates by Gender/Ethnicity/Race

Ethnic Category	Sex/Gender			
	Females	Males	Unknown	Total
Hispanic or Latino	0	6	0	6
Not Hispanic or Latino	64	120	0	184
Unknown	0	0	0	0
Ethnic Category: Total of all subjects	64	125	0	190
Racial Category				
American Indian or Alaskan Native	0	0	0	0
Asian	0	0	0	0
Black or African American	9	20	0	29
Native Hawaiian or other Pacific Islander	0	0	0	00
White	56	105	0	161
More than one race	0	0	0	0
Unknown	0	0	0	0
Racial Category: Total of all subjects	64	125	0	190

Ethnic Categories: **Hispanic or Latino** – a person of Cuban, Mexican, Puerto Rican, South or Central American, or other Spanish culture or origin, regardless of race. The term “Spanish origin” can also be used in addition to “Hispanic or Latino.”

Not Hispanic or Latino

Racial Categories: **American Indian or Alaskan Native** – a person having origins in any of the original peoples of North, Central, or South America, and who maintains tribal affiliations or community attachment.

Asian – a person having origins in any of the original peoples of the Far East, Southeast Asia, or the Indian subcontinent including, for example, Cambodia, China, India, Japan, Korea, Malaysia, Pakistan, the Philippine Islands, Thailand, and Vietnam. (Note: Individuals from the Philippine Islands have been recorded as Pacific Islanders in previous data collection strategies.)

Black or African American – a person having origins in any of the black racial groups of Africa.

Native Hawaiian or other Pacific Islander – a person having origins in any of the original peoples of Hawaii, Guam, Samoa, or other Pacific Islands.

White – a person having origins in any of the original peoples of Europe, the Middle East, or North Africa.

17.0 Pathology Considerations/Tissue Biospecimens NA**18.0 Records and Data Collection Procedures**

18.1 Submission Timetable

Data submission instructions for this study can be found in the Data Submission Schedule.

18.2 Survival Follow-up

N/A. See [Section 4](#).

18.3 CRF completion

This study will use Medidata Rave for remote data capture (rdc) of all study data. Data collection for this study will be done exclusively through the Medidata Rave clinical data management system. Access to the trial in Rave is granted through the iMedidata application to all persons with the appropriate roles assigned in Regulatory Support System (RSS). To access Rave via iMedidata, the site user must have an active account and the appropriate Rave role (Rave CRA, Read-Only, Site Investigator) on either the organization roster at the enrolling site.

18.4 Site responsibilities

Each site will be responsible for ensuring that all materials contain the patient's initials, MCCC registration number, and MCCC protocol number. Patient's name must be removed.

18.5 Supporting documentation

This study requires supporting documentation for diagnosis for all cohorts and relapse prior to study entry for Cohort C and Cohort D. These documents should be submitted within 14 days of registration.

Supporting documentation for diagnosis will include either a pathology report or a laboratory report demonstrating multiple myeloma (including SPEP, UPEP, FLC, Serum and Urine Immunofixation, Bone Marrow Biopsy and Aspirate, skeletal bone survey, PET scan, Plasma Cell Proliferation and Assessment and FISH). These reports should be uploaded into the Supporting Documentation: Baseline form within 14 days of registration.

For relapse of disease prior to study entry, supporting documentation includes the evidence needed to determine the patient's relapse prior to enrollment. These documents should be uploaded into the Supporting Documentation: Baseline form within 14 days of registration.

For response to treatment, supporting documentation may include SPEP, UPEP, FLC, Serum and Urine Immunofixation, Bone Marrow Biopsy and aspirate, skeletal bone survey, and PET scan. These documents should be uploaded into the Supporting Documentation form.

For patients who progress after study therapy supporting documentation may include any of the following: SPEP, UPEP, FLC, serum and urine immunofixation, bone marrow biopsy and aspirate, skeletal bone survey, and PET scan. These documents should be uploaded into the Supporting Documentation form.

18.6 Labeling of materials

Each site will be responsible for ensuring that all materials contain the patient's initials, MCCC registration number, and MCCC protocol number. Patient's name must be removed.

18.7 Overdue lists

A list of overdue forms and outstanding queries will be available in Rave through the Rave Task Summary. In addition to this, the Overdue Materials report will be distributed monthly by the data manager.

